The proposed study will use the DERRI to identify diabetic patients at high-risk of readmission who will be provided with a novel intervention designed to reduce hospital utilization rates within 30 days of discharge. This multifactorial intervention builds on techniques effectively used in other inpatient populations, specifically, patient-centered discharge education, peri-discharge coordination of care, and post-discharge support by nurses and community health workers (CHWs), and adapts them to patients with diabetes.[2-8] In addition, the intervention includes adjustment of diabetes therapy upon discharge based on the admission A1c, which improves post-discharge glycemic control and is associated with a lower risk of 30d readmission.[9, 10]

Readmission Pilot Trial

We propose a pilot randomized controlled trial to address the following aims:

Aim 1: To explore the feasibility, acceptability, and efficacy of a novel multifactorial intervention designed to reduce all-cause readmission or ED visit rates within 30 days of discharge among hospitalized patients with diabetes who are identified as high risk based on the DERRI

Aim 2: To prospectively validate the readmission risk predictions generated by the DERRI

The usual care control group will provide the baseline risk of 30d post-discharge hospital utilization in the patient population predicted to be at high risk by the DERRI. Furthermore, we will prospectively follow patients who are predicted to be at lower risk to validate the DERRI in this population.

5) Background

Significance

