All data collected by the research team will be considered part of the participant's confidential record. Data collected on paper from research participants will be placed in a locked file cabinet in the GCRC within 24 hours. The destruction date of paper files will be at least 7 years from the termination of the study and will be authorized by the PI. Access to research and confidential records will be limited to clinical investigators and research coordinators.

h) Data Management

Statistical analysis: Distributions of the data will be assessed by descriptive statistical and graphical methods. To assess the randomization procedure, baseline values of all variables will be compared between the intervention and usual care group. Between-group differences for continuous variables will be compared using the Wilcoxon test. Proportions will be compared between groups using the chi-square test or exact tests when expected cell counts are less than 5. The primary outcome of 30d readmission rate will be compared between intervention and control groups with the chi-square test. Point estimates of 30d readmission rates will be obtained and presented with 95% confidence intervals. Time to readmission will be estimated by Kaplan-Meier curve and compared between groups by log-rank test. The composite of 30d readmission and ED visits will be compared by Cox regression model. Continuous secondary outcomes will be compared using Wilcoxon test. Categorical secondary outcomes will be compared using chi-square test. The primary analyses for all outcomes will be performed in the intention-to-treat (ITT) population. Secondary analyses for all outcomes will be performed in a per-protocol population restricted to subjects who complete at least one follow-up phone call. In addition, outcomes will be assessed for differences by the number of follow-up phone calls

Readmission Pilot Trial

completed (dose-response analysis). Lastly, all outcomes will be assessed in the ITT subgroup of subjects with a baseline A1c >7%. Statistical significance will be claimed at an alpha level of 0.05.

Power analysis: The sample size for Phase 2A was based on an expected drop-out and post-enrollment exclusion rate of 25% as well as the capacity of the research team. Because this is a pilot feasibility trial, the study is not powered to detect a difference in outcomes.

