All participants will be given unique study identifiers. Data with personally identifiable information will be stored securely on HIPAA-compliant TUH servers. Data exported for statistical analysis will be stripped of personal identifiers. Participants will be free to withdraw from the study at any time.

Phase A: To minimize the risk of hypoglycemia, only patients with uncontrolled diabetes according to an elevated A1c will have their diabetes therapy adjusted. Patients will be followed closely for 30 days after discharge with weekly phone calls, and glycemic control will be monitored. Patients discovered to have hypoglycemia or hyperglycemia will be referred for adjustment of their diabetes therapy by the PI, an Endocrinologist.

A Data Safety Officer (DSO) not otherwise directly involved with the research, a senior diabetologist and clinical investigator with inpatient diabetes research experience, [name] at the University of Colorado Denver, will review de-identified data every 3 months. Adverse events will be reported to the Temple Institutional Review Board and the NIH according to standard policy.

Readmission Pilot Trial

Phase B: Every effort will be made to ensure that all qualitative data are kept confidential. The digital audio files produced will be used only for the purpose of this study. They will be downloaded from the recording device and stored on a secure computer in the research assistant's private GCRC office. The audio files will be transcribed. In the transcript, each subject will be assigned an anonymous study identification number. The data file linking personal identifiers and study identification numbers will be stored separately from the transcript data. The files with the transcribed data will have no personal identifiers and will contain no information linking an individual participant with their study code. The DSO will not monitor Phase B because there is minimal risk involved with this phase.

The following procedures will be implemented to ensure data safety and adequate monitoring:

- The PI will monitor study progress on an on-going basis and ensure the protection of human subjects, including the safe and secure collection and storage of data. An annual review will include assessment of accrual, adverse events, and data management practices.

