- All data linking subjects to de-identified information will be maintained in a password-protected, encrypted computer with access limited to only those research personnel with a reasonable need to have such information.
- Reporting Adverse Events
 - Definitions:
 - Adverse Event: Any medical problem that manifests during the course of the study, as a result of an assessment or an aspect of the study intervention.
 - Serious Adverse Event: An adverse event that is fatal or life-threatening, results in significant or persistent disability, or requires hospitalization.
 - Unexpected Serious Adverse Event: Any event that has not been described in the protocol or informed consent document.
 - Reporting Mechanisms
 - All adverse events will be discussed at weekly operations meetings and reported to the PI and IRB according to standard operating procedure.
 - Serious adverse events (expected and unexpected) will be reported to the PI immediately and to the IRB in writing within 1 business day.
 - The NIH procedure for Reporting Clinical Study Serious Adverse Events will be followed for the reporting of expected and unexpected serious adverse events to the study sponsor.
- The DSO will review the protocol and study procedures every 3 months to ensure that proper regulatory processes are followed during study execution. In this role, he will:

Readmission Pilot Trial

- Review all adverse events or complications related to the study and make recommendations for protocol changes if indicated.
- Assure scientific integrity of the study by providing regulatory oversight.
- Assure participants' confidentiality and informed consent by reviewing study procedures.
- Provide advice, as requested, on quality assurance measures.

k) Withdrawal of Subjects

Subjects may withdraw at will at any time. Subjects may be withdrawn from the trial at the discretion of the PI due to a safety concern, if judged non-compliant with trial procedures, or pregnancy during the primary follow-up period (30 days after discharge). For subjects in the intervention group, we will obtain permission to continue to collect data from the electronic medical record.

9) Risks to Subjects

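### Continued record review after withdrawal is planned for the intervention arm only, so 30-day outcome completeness can depend on allocation

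*Protocol*

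**What the plan says.** Section 8(k) of the protocol opens with a rule for everyone: "Subjects may withdraw at will at any time". Section 8(j) says the same: "Participants will be free to withdraw from the study at any time". Section 8(k) also lets the investigator withdraw subjects for safety, non-compliance or pregnancy. It then turns to one group: "For subjects in the intervention group, we will obtain permission to continue to collect data from the electronic medical record".

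The outcome affected is the primary one. Section 8(h) states: "The primary outcome of 30d readmission rate will be compared between intervention and control groups with the chi-square test", and "The primary analyses for all outcomes will be performed in the intention-to-treat (ITT) population".

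The other two groups carry Aim 2. Section 4 states: "The usual care control group will provide the baseline risk of 30d post-discharge hospital utilization" among patients the DERRI predicts to be at high risk, and adds: "we will prospectively follow patients who are predicted to be at lower risk to validate the DERRI in this population".

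The only loss figure is in the power paragraph of section 8(h), an "expected drop-out and post-enrollment exclusion rate of 25" per cent. It pools two kinds of loss and is not split by group.

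**The concern.** In a randomised comparison, the rule for collecting the primary outcome after a subject leaves should be the same in both arms. Here a withdrawn intervention subject has a stated route to the 30-day outcome, through the medical record, and a withdrawn usual-care subject has none. Completeness of the outcome can then depend on allocation, and an intention-to-treat label does not restore data that were never collected. An analysis plan cannot repair this later, because access to records after withdrawal is settled by consent and study conduct.

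Aim 2 has a related weakness. The high-risk baseline rate comes from usual care and the lower-risk rate from the observational cohort. Neither group has a stated rule for subjects who withdraw, so the observed rates used to check the DERRI may have gaps.

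**Working it through.** The protocol states no figure for this point, so there is none to reproduce. The check is mainly a comparison of the text across groups.

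**Who can leave, and what follows**

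| Group (planned size, section 8(c)) | May withdraw | 30-day outcome source during follow-up (section 8(f)) | Stated rule for continued record review (section 8(k)) |
|---|---|---|---|
| Intervention (60) | Yes | Phone and medical record | Permission to be sought |
| Usual care (60) | Yes | Phone and medical record | None |
| Low risk (180) | Yes | Temple record, then contact with the subject if no visit is found | None |

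**Is the gap filled elsewhere?** The waiver in section 8(a) is for identifying candidates. Section 11 says that a HIPAA Authorization was submitted but does not give its scope after withdrawal. Sections 14 and 15 refer to institutional consent guidance. None of these states a rule for the other two groups.

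**Effect of one unknown outcome.** A missing binary outcome may be 0 or 1, so it widens the possible range of a group's rate by 1/n.

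- Usual care: 1/60 = 0.0167, or 1.7 points. The between-arm difference widens by the same amount.
- Low risk: 1/180 = 0.0056, or 0.6 points.

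**Why the direction is open.** Suppose *w* of 60 usual-care outcomes are lost and the intervention arm is complete. Let *p* be the readmission risk in those who stay and *r* the risk in those who leave. The true rate is [(60 − w)p + w·r]/60.

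- If missing subjects are dropped, the bias in the control rate is p − true = (w/60)(p − r).
- If they are counted as not readmitted, the bias is −(w/60)r.

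Take p = 21% as an assumption. It is the top of the 14.4–21.0% range that section 5 gives for diabetic patients in general, not a figure for the DERRI high-risk group. Take w = 3 or 6 (5% or 10%), also assumed.

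| Assumption | w = 3 | w = 6 |
|---|---|---|
| Dropped, r = p | 0 | 0 |
| Dropped, r = 2p = 42% | (3/60)(−21) = −1.05 points | (6/60)(−21) = −2.1 points |
| Dropped, r = p/2 = 10.5% | (3/60)(10.5) = +0.5 points | (6/60)(10.5) = +1.05 points |
| Counted as no event, r = p | −(3/60)(21) = −1.05 points | −(6/60)(21) = −2.1 points |

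The sign changes with the risk of those who leave and with how missing outcomes are handled. The 25% is not used as a withdrawal rate, because it includes post-enrollment exclusions.

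**The case against.** The sentence in section 8(k) says neither *only* nor *after withdrawal*. Only intervention subjects have a programme of calls and therapy review to leave while data collection continues, so the sentence may be meant for those who stop the programme but remain in the study. For the other groups, leaving the study comes close to declining data collection altogether. The protocol also does not say that record review stops for withdrawn controls, and the consent form and HIPAA Authorization, which are not shown, may cover everyone. Usual care and low risk have little study contact between baseline and follow-up at about week 5 or later, so few may withdraw. Finally, this is a pilot with no power claim.

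Most of this stands as a limit on size. It does not remove the asymmetry. If the sentence concerns stopping the programme, the other two groups still have no stated rule. If the consent documents cover all groups, naming one group in section 8(k) is misleading and should be corrected. The lack of power means that no significance verdict is in question, but efficacy is part of Aim 1 and readmission rates will be reported with 95% confidence intervals.

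The Aim 2 part is the weaker one: the low-risk group is a single observational cohort, so its problem is incompleteness, not imbalance between arms. Ascertainment after withdrawal may also be incomplete in the intervention group, because permission can be refused and the record can miss visits to other institutions.

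**Conclusion.** The concern holds and should be fixed. Section 8(k) plans permission for continued record review in one randomised arm and gives the other arm and the low-risk cohort no equivalent. Followed as written, this can make completeness of the primary outcome depend on allocation.

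No bias of any particular size or direction is claimed; the number of withdrawals in each group decides how much this matters, and the protocol does not give it. The conclusion rests on reading the sentence as the rule for subjects who leave, which its place in the withdrawal section supports, and on no unseen consent text already covering every group. Confidence is medium for those reasons.

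**What to change.** Replace the last sentence of section 8(k) with one that applies to all three groups, for example: *Subjects in every study group will be asked to allow the study team to keep reviewing their electronic medical record for outcomes after they withdraw.* If the sentence was meant for subjects who stop the programme without leaving the study, state that as well. If the consent form and HIPAA Authorization already give this permission for all groups, say so in section 8(k); otherwise add a matching sentence to the consent form.

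Two secondary additions would help readers: report withdrawals and availability of the 30-day outcome by group, and note that record review after withdrawal can miss visits elsewhere in every group.

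The cost is one sentence in the protocol and possibly one in the consent form. Record review is already planned in every group, and no sample size or analysis changes.
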